died within 7 days compared to the SOC arm (1% vs 4%, P=0.018, respectively) and also at 30 days (9% vs 15%, P=0.066), respectively. There were 2 bacterial brain infections with 30 days in the MISTIE arm and none in the SOC arm. The MISTIE arm and SOC arm had comparable symptomatic brain bleeds with 72 hours from the last thrombolytic dose (2% vs 1%, P=0.325). However, asymptomatic brain bleeds within 72 hours from the last thrombolytic dose was significantly higher in the MISTIE arm. There were fewer serious adverse events reported in the MISTIE arm compared to the SOC arm (126 events vs 142, P=0.012), which was statistically significant. The authors reported that an exploratory analysis of clot removal did show an association between extent of removal and a lower mRS score (0-3), possibly due to the benefit of the procedure or due to unmeasured confounding effects. Furthermore, the authors concluded that there were few negative consequences to MISTIE, and it was safe with regards to serious bleeding and infection. The procedural risks were also reported as comparable between the two arms.

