The complications particularly related to the procedure include bleeding, infection, or damage to surrounding structures during the creation of the cranial access or placement of the sheath. During evacuation of the hemorrhage with the Artemis Device, there is the possibility of inducing or encountering an additional hemorrhage in the operative bed. In a retrospective multicenter study of the Apollo procedure for the treatment of ICH, re-bleeding was encountered in 2 of 29 subjects (6.9%).⁵⁶ There may be residual fluid or blood requiring additional surgery in the future.

The risk related to the general anesthetic in this patient population is estimated to be approximately 1 – 5% for major morbidity and mortality (e.g. airway management issues, aspiration, hypotension or drug reaction), given that their American Stroke Association score would typically be 4 or 4e in this category of patients.^{57,58} A thorough risk analysis was performed as part of design control recommendations of the Quality System Regulation (21 CFR 820).

Best medical management (MM) will be provided as specified in the AHA/ESO guidelines.^{18,59} As such, for subjects randomized to the MM arm of the study, there is no additional risk. With the natural history of ICH/IVH and standard of care, there are expected medical events, or expected adverse experiences, that are listed below. Since these medical events are expected in the disease process or after MM, the events are thus expected to occur in any patients with the disease irrespective of the treatment arm. Best medical management (MM) will be provided as specified in the AHA/ESO guidelines.^{19,60} As such, for subjects randomized to the MM only arm of the study, there is no additional risk.

EXPECTED EVENTS	
Nervous System	Other Systems
Cerebral Edema and Mass Effect	Acute Kidney Injury
Brain Stem Compression	Acute Respiratory Distress Syndrome
Brain Herniation	Aspiration
Brain Re-bleeding near Initial Hemorrhage Site	Catheter-related vascular infections
Catheter Tract Bleeding/Hemorrhage Enlargement	Deep Vein Thrombosis
Cerebral Infarction	Dysphagia
Cerebritis	Fever/Hyperthermia

Coma	Hyponatremia
Death	Hypoxia
Decreased Level of Consciousness	Hypercapnia
Delirium	Hyperglycemia/Hypoglycemia
Diaschisis	Hypertension (Induced or Not Induced)
Elevated ICP	Hypotension (Induced or Not Induced)
Headache	Impaired Nutritional Status
Hydrocephalus	Infectious Complications
Intracranial Abscess	Nausea

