6.7.1 Preparation for Treatment

Subjects randomized to the control group will receive best MM for ICH as determined by the stroke physician. All physicians will follow current AHA/ESO guidelines for the treatment of ICH.^{18,59} {Hemphill, 2015 #1049;Steiner, 2014 #2487} Subjects randomized to MIS will also receive best MM in addition to the procedure. Reversible coagulopathies at presentation will be corrected as determined by the physician managing the subject. Ventricular drains will be placed as deemed necessary by the managing interventional team to manage ICPs.

MIS will be performed under general anesthesia. The MIS procedure must occur within 72 hours of ictus. The subject should be prepared for the planned intervention according to standard hospital procedures. MIS will be performed as described below (6.7.4)

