- Symptomatic Re-Hemorrhage or New Hemorrhagic Event: Any new intracranial hemorrhage or increase in size of pre-existing hemorrhage (IPH, IVH or extra-axial bleed) within 30 days associated with an NIHSS increase of ≥ 4 or a GCS decrease > 2 persisting for at least 24 hours, requiring emergency surgical decompression or resulting in death.
- Symptomatic Evolution of Perihematomal Edema: Edema with increased mass effect or uncontrolled ICPs within 30 days requiring emergency surgical decompression NOT related to new or increased hemorrhage (i.e. edema related) associated with an NIHSS increase of ≥ 4 or a GCS decrease > 2 persisting for at least 24 hours, requiring emergency surgical decompression or resulting in death.
- Symptomatic Ischemic Stroke: A new ischemic stroke (ipsilateral, contralateral; contiguous with bleed/operative site or remote; cortical, subcortical or perforator distribution) within 30 days associated with an NIHSS increase of ≥ 4 or a GCS decrease > 2 persisting for at least 24 hours, requiring emergency surgical decompression or resulting in death.
- Surgical complications related to MIS: Surgical site infection, brain abscess or confirmed meningitis, or documented complication(s) deemed specifically related to the procedural anesthetic (medication, access or intubation related) within 30 days.

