12.2 Stopping the Trial Based on Interim Safety Data

The DSMB will receive periodic safety reports of all reported AEs and SAEs. In addition, the following specific endpoints will be assessed by the medical monitor and presented:

- Death (all cause) within 30 days of enrollment
- Death within 7 days of enrollment: Immediate periprocedural death
- Symptomatic Re-Hemorrhage or New Hemorrhagic Event: Any new intracranial hemorrhage or increase in size of pre-existing hemorrhage (IPH, IVH or extra-axial bleed) within 30 days associated with an increase of 4 or more points on the NIHSS or GCS decrease > 2 persisting for at least 24 hours, requiring emergency surgical decompression or resulting in death
- Symptomatic Evolution of Perihematomal Edema: Edema with increased mass effect or uncontrolled ICPs within 30 days requiring emergency surgical decompression NOT related to new or increased hemorrhage (i.e., edema related) associated with an increase of 4 or more points on the NIHSS or GCS decrease > 2 persisting for at least 24 hours, requiring emergency surgical decompression or resulting in death
- Symptomatic Ischemic Stroke: A new ischemic stroke (ipsilateral, contralateral; contiguous with bleed/operative site or remote; cortical, subcortical or perforator distribution) within 30 days associated with an increase of 4 or more points on the NIHSS or GCS decrease > 2 persisting for at least 24 hours, requiring emergency surgical decompression or resulting in death
- Surgical complications related to MIS: Surgical site infection, brain abscess or confirmed meningitis, or documented complication(s) deemed specifically related to the procedural anesthetic (medication, access or intubation related) within 30 days

Additional details regarding the DSMB structure and stopping rules will be included in the DSMB charter.

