11.2. Analysis of Adverse Events

Adverse events will be coded using the MedDRA dictionary. The number and percentage of subjects with AEs and SAEs will be summarized by body system and preferred term. Each subject will be counted only once within a category. The specific categories analyzed will be those that are reported by at least three (3) percent of the subjects. The Clinical Events Committee adjudicated data supersedes the investigator reported data in all analyses of adverse events.

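### Brain abscess and meningitis are specific safety events only when related to MIS, so the category gives no control count for infections that the protocol expects in both arms

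*Protocol*

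**What the plan says.** Protocol 7.6.1 names six specific events for a detailed form and narrative, and 7.6.1.1 has the medical monitor review them as they are reported. Death, re-hemorrhage, perihematomal edema and ischemic stroke are defined without reference to treatment. The sixth is tied to the procedure: "Surgical complications related to MIS: Surgical site infection, brain abscess or confirmed meningitis", together with complications attributed to the procedural anesthetic, within 30 days. Section 12.2 repeats the list for the DSMB, stating that "the following specific endpoints will be assessed by the medical monitor and presented". The same section also says: "The DSMB will receive periodic safety reports of all reported AEs and SAEs".

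The expected-event table in Protocol Section 3 includes intracranial abscess, meningitis and ventriculitis. The text introducing it says that "the events are thus expected to occur in any patients with the disease irrespective of the treatment arm". Section 6.7.1, which covers both groups, says: "Ventricular drains will be placed as deemed necessary by the managing interventional team to manage ICPs". Exclusion criterion 1f likewise permits a drain for pressure management, and Section 4.3 rules out crossover.

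SAP 11.2 promises AE and SAE counts and percentages by body system and preferred term, then adds: "The specific categories analyzed will be those that are reported by at least three (3) percent of the subjects".

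**The concern.** Five of the six events can be counted in any randomized patient. The sixth holds the intracranial infections, and entry depends on having had the study procedure. The protocol itself gives a route to such an infection in an MM patient: the disease and its care, a ventricular drain, or the emergency decompression that the other event definitions foresee without reference to arm. An MM patient with drain-related meningitis gets no mandatory narrative and no place in the category.

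At stake is how MIS infections are interpreted. If several are recorded, the natural question is how many would have occurred anyway in patients this ill, many of whom may have had a drain. The specific-event category cannot answer that. The general AE tables could, but the 3% rule may remove an uncommon infection from the comparison. In a device trial with a safety objective, ascertainment that depends on the arm is worth removing.

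**Working it through.** The plan states no figure on this point, so there is none to reproduce. The check sets the provisions side by side, then looks at the threshold.

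**1. Can an MM case enter the category?** The event must be related to MIS (7.6.1, 12.2). Crossover is not permitted (4.3), so an MM patient treated per protocol has no MIS to which an infection can relate. The MM count is zero whatever the true MM rate. The only exception is an MM-randomized patient who receives MIS in breach of protocol.

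**2. Can an MM case enter another specific event?** Only as a death within 30 days of enrollment. No other item covers infection.

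**3. Are MM cases foreseen?** Yes, by the Section 3 table, and drains are allowed without limit by arm (6.7.1 and criterion 1f). This holds for brain abscess and meningitis. Surgical site infection is not named in the table and, like anesthetic complications, belongs mainly to the surgical arm.

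**4. Does SAP 11.2 close the gap?**
- Overall threshold: 0.03 × 500 = 15 subjects at the maximum sample size; 0.03 × 200 = 6 at the minimum.
- Allocation 2:1 at 500: 500 × 2/3 = 333 MIS and 167 MM.
- If the 3% applies to all subjects, a term seen in 14 of 333 MIS patients (4.2%) and no MM patient falls short, since 14/500 = 2.8%.
- If it applies within an arm, 0.03 × 333 = 9.99. A term seen in 9 MIS patients (9/333 = 2.7%) still falls short.

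The SAP does not say which denominator is meant, or whether rarer terms are still summarized by arm. The gap is therefore possible, not certain.

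**5. How many MM cases might be left out?** The documents give no MM infection rate for MIND. Under assumed rates r, with 167 MM patients, the expected number is 167r and the chance of at least one is 1 − (1 − r)^167:

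| Assumed r | Expected MM cases | P(at least one) |
|---|---|---|
| 0.5% | 0.8 | 57% |
| 1% | 1.7 | 81% |
| 2% | 3.3 | 97% |
| 3% | 5.0 | 99% |

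These show the range only. The one observed figure in the protocol is from the phase III catheter-evacuation trial it summarizes (MISTIE III): "There were 2 bacterial brain infections with 30 days in the MISTIE arm and none in the SOC arm". That trial's outcome, bacterial brain infection at 30 days, is described without a condition on the procedure, so its control arm had a count, which was zero.

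**6. Is the MIS count itself stable?** Section 7.6.1.3 does not expect events later than 7 days after the procedure to be judged procedure-related, while the category runs to 30 days. An infection arising between day 8 and day 30 may be graded unrelated and left out. The same may happen with an infection attributed to a concurrent drain.

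**The case against.** The strongest reply is that nothing depends on the category and the data exist elsewhere. The DSMB receives all AEs and SAEs, weighs all available evidence and can request further analyses (7.6.1.1). The stopping rules to be developed concern the primary safety endpoint, 30-day mortality. SAP 11.3 makes other safety comparisons secondary and keeps them out of labeling claims. The category is openly labelled as MIS complications, and the board includes neurovascular specialists and a statistician. SAP 11.2 can also be read as summarizing every term and limiting only the formal analysis. All of this stands, and it limits the weight of the point.

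A reader might go further and infer that the DSMB will see a false infection signal against MIS. With equal assumed rates of 3% at full enrollment, the category would read 10 vs 0 (two-sided Fisher p = 0.035), while counting both arms would give 10 vs 5 (p = 1.0). The arithmetic is right, but the documents do not support the inference. Neither document prescribes a by-arm display or test of this category, and the DSMB charter is not available. The equal rate of 3% is assumed. At 2% the contrast is 7 vs 0 (p = 0.10). In MISTIE III, where both arms had a count, the result was 2 vs 0, so a zero in controls need not be an artefact.

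What the reply does not remove is the missing definition, narrative and category count for MM cases, or the doubt over SAP 11.2.

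**Conclusion.** The point holds as a limited, inexpensive improvement. By wording alone, and assuming no crossover, no MM brain abscess or meningitis can enter the specific-event category. A non-fatal case is left to the general AE/SAE reports, and SAP 11.2 may not analyze it by arm if fewer than 15 of 500 subjects report it. The mismatch between 7 and 30 days may also leave out late MIS infections.

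The primary efficacy analysis, the primary safety analysis and the stopping rules are unaffected. It would be wrong to conclude that MM infections are hidden from the DSMB or that the final report cannot compare the arms. The data are collected, and only their structured ascertainment and guaranteed reporting differ by arm. The effect cannot be sized, since every infection rate used for MIND above is an assumption.

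**What to change.** In Protocol 7.6.1 and 12.2, split the bullet in two:

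- *Intracranial infection: brain abscess or confirmed meningitis within 30 days of randomization, either arm, regardless of cause.* Record relatedness to MIS, ventricular drain or other neurosurgery as an attribute, so that entry does not depend on the 7-day expectation in 7.6.1.3.
- *MIS surgical-site infection and procedural-anesthetic complications within 30 days*, kept as a separate MIS-only item.

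In SAP 11.2, state that intracranial infection is reported by arm (number, percentage, difference with 95% confidence interval) whatever its frequency, with the MIS-related subset shown beside it.

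The cost is a change to one bullet in two protocol sections, one sentence in the SAP, and a few more narratives for MM patients. No visit or test is added. Showing the MIS-related subset keeps the information that the present category was meant to give.

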The overall risks associated with the procedure depend on a number of factors including, but not limited to, the device, anesthesia, disease condition and medical management. The primary risks to subjects in this study are associated with the minimally invasive surgical (MIS) procedure and the associated general anesthetic. Imaging performed throughout the course of the study, while specified in the protocol, falls within the standard of care for the initial evaluation and follow-up of patients with intracranial hemorrhage. The MIS procedure is performed in a manner which is similar to that of other neuroendoscopic procedures and the associated risks are similar. In brief (see Section 6.7 for a detailed description of the procedure), the MIS procedure involves the creation of a burr hole/1 – 2 cm craniectomy and dural incision. An endoscopic sheath is then placed through the access site into the hematoma under imaging control using neuronavigation. Under endoscopic guidance, the hemorrhage is evacuated using the Artemis Device. Following the evacuation, the endoscope and Artemis Device are removed. Intraoperative CT imaging is performed to assess the remaining hemorrhage volume and to assess for immediate procedural complications. Ultrasound may also be used during the procedure to evaluate removal of the hematoma. Based on the intra-operative CT imaging, either an additional pass(es) is made or the procedure is terminated. Following the procedure, all equipment is removed and the cranial access is closed in a standard manner.

The potential clinical risks that may be associated with the use of Artemis Device or with the procedure include, but may not be limited to:

Hematoma expansion	Increased blood pressure
Fever	Infections
Headaches	Seizures
Vomiting	Intraventricular hemorrhage
Hyperglycemia	Hydrocephalus
Edema	Thromboembolic events
Re-bleeding	Decreased consciousness
Death	Craniotomy
Bleeding	Unintended Removal of Tissue leading to Neurological and/or sensory deficit

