7.6.1.1 Analysis of Adverse Events

A medical monitor will review these specific categories of events as they are reported. The medical monitor has the authority to alert the DSMB at any time if a potential safety issue arises. If at any point, these reviews raise any safety concerns, the DSMB will be empowered to suggest that the study be placed on hold and request additional analyses of the study dataset. At the end of each DSMB meeting, the board shall recommend study (i) continuance according to protocol, (ii) modification of the protocol, or (iii) early study termination. The DSMB shall base their recommendations on all available evidence and their collective expertise and judgement. Safety stopping rules for the primary safety endpoint will be developed and used to help the DSMB make its safety assessments. Additional details regarding the DSMB structure, frequency of meetings and stopping rules will be included in the DSMB charter.

In addition to the reporting requirements noted above, pre-defined AE/SAEs will be evaluated by the Clinical Events Committee (CEC) for an independent analysis at regularly scheduled meetings according to the CEC Charter. Redacted source documents will be collected for events requiring adjudication and for other events where the medical monitor deems necessary.

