10.1 Sample Size Estimation for the Primary Outcome

The proposed study is a randomized controlled study designed to demonstrate the efficacy of MIS to improve clinical outcomes across the entire population of patients with supratentorial ICH, as well as to evaluate effect sizes within major anatomical sub-groups (e.g., deep vs. lobar hemorrhage) and cohorts (e.g. age, presenting GCS). In addition, the treatment arm will provide, for the first time, a prospective, independently adjudicated, characterization of the technical outcomes and complication rates associated with the Artemis MIS procedure.

This design provides 81% power for a cumulative odds ratio of 1.7 for the Day 180 mRS. The design's overall one-sided Type I error rate is 2.5%.

The maximum study sample size is 500 subjects and the minimum sample size is 200 subjects. The final study sample size is estimated to be low if the treatment effect is small and the study could be stopped for futility or if the treatment effect is large and the study could be stopped for expected success. The final study sample size will be high if the evidence for the treatment effect is inconclusive.

The Day 180 mRS distribution used for sample size estimation was based on control arm data from the following published studies: MISTIE⁴⁸, STICH¹³, and SICHPA⁶⁴. The distribution of mRS functional outcomes utilized in the sample size estimation is provided in Table 3.

Table 3. Distribution of mRS Functional Outcomes

mRS Distribution	0	1	2	3	4	5/6
MM	3%	10%	7%	7%	14%	59%
MIS	5%	15%	10%	9%	16%	46%

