11.2.2 Clinical Events Committee (CEC)

The Clinical Events Committee (CEC) is made up of independent medical doctors who are not participants in the study. The CEC is charged with the development of specific criteria used for the categorization of clinical events and clinical endpoints in the study which are based on the protocol.

At the onset of the study, the CEC will establish explicit rules outlining the minimum amount of data required, and the algorithm followed in order to classify a clinical event. While the CEC review of adverse events specific to the interventional procedure will unblind the members, all members of the CEC will be blinded to the overall primary results of the study.

The CEC will review and adjudicate appropriate clinical events, mainly related to the device and to the study endpoints. The CEC will also review and rule on all deaths that occur throughout the study. The safety process flow and a web-based electronic database will be provided to CEC members for case review and adjudication. The designated Penumbra staff who are responsible for reviewing safety data on an ongoing basis will coordinate collection of information for the event dossier.

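### The defined-event list omits deficit from tissue removal or access injury, and the SAP's 3% rule does not exempt defined events

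*Protocol*

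**What the plan says.** Protocol section 3 sets out the risks of the device and procedure. Its list of potential clinical risks includes "Unintended Removal of Tissue leading to Neurological and/or sensory deficit". The text after the list names bleeding and infection as complications particular to the procedure, together with "damage to surrounding structures during the creation of the cranial access or placement of the sheath".

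Protocol 7.6.1 then lists the specific adverse events that need a detailed form and narrative. The surgical category reads "Surgical complications related to MIS: Surgical site infection, brain abscess or confirmed meningitis, or documented complication(s) deemed specifically related to the procedural anesthetic", within 30 days. Section 7.6.1.1 adds: "A medical monitor will review these specific categories of events as they are reported". Section 12.2 repeats the list for the DSMB: "the following specific endpoints will be assessed by the medical monitor and presented".

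Protocol 10.1 says that the treatment arm will provide a prospective, "independently adjudicated, characterization of the technical outcomes and complication rates associated with the Artemis MIS procedure". Section 11.2.2 sets the CEC's scope: "The CEC will review and adjudicate appropriate clinical events, mainly related to the device and to the study endpoints".

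SAP 11.2 summarizes AEs and SAEs by body system and preferred term, and then says: "The specific categories analyzed will be those that are reported by at least three (3) percent of the subjects". It does not mention the defined events of Protocol 7.6.1.

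**The concern.** The protocol names a direct surgical harm to the brain as a risk, and then defines surgical complications so that only infection and anesthetic events qualify. Being on the list brings three things: a narrative, medical-monitor review as events are reported, and a separate line before the DSMB. A deficit caused by removing or traversing brain tissue is assured none of them unless it also meets another definition.

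The final report raises a second, separate question. Procedural complications occur in one arm only and may be uncommon. A frequency cut-off with no stated denominator and no exemption for defined events could leave them out of the analyzed categories. Complications of the MIS procedure are among the things that Protocol 10.1 says the treatment arm will characterize.

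**Working it through.** **Part 1: the event list (comparison of text, no arithmetic).** The six categories in 7.6.1, repeated in 12.2, set against the risks in section 3:

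| Defined event | Covers deficit from tissue removal or access injury? |
|---|---|
| Death within 30 days | Only if fatal |
| Death within 7 days | Only if fatal |
| Symptomatic re-hemorrhage or new hemorrhage | Only if it presents as qualifying bleeding |
| Symptomatic perihematomal edema | Only if it presents as qualifying edema |
| Symptomatic ischemic stroke | Only if it presents as a qualifying infarct |
| Surgical complications of MIS | No: infection and anesthetic events only |

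The word *access* does occur in the last category, but inside the parenthesis that qualifies the anesthetic. It does not reach cranial access. The gap is therefore direct tissue or tract injury without qualifying bleeding, edema, infarct or death.

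Two other routes do not clearly close it. The definition of an unanticipated device effect (7.6.1.2) covers effects not already identified in the protocol, and section 3 identifies this one. Section 7.6.1 also lets an expected progression of the condition be recorded as an AE rather than an SAE. An unblinded investigator could classify a new deficit after evacuation that way.

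**Part 2: the 3% rule.** Inputs:
- Maximum N = 500 and 2:1 allocation (Protocol synopsis), so 500 × 2/3 = 333 MIS subjects.
- Minimum N = 200, with 133 MIS subjects (Protocol synopsis; SAP section 2).
- Cut-off of 3% (SAP 11.2), with the denominator not stated.
- True MIS rates of 3%, 4% and 5%. These are assumptions: the documents give no rate for this complication.

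Cut-offs in subjects: 0.03 × 500 = 15; 0.03 × 333 = 9.99, so 10; 0.03 × 200 = 6; 0.03 × 133 = 3.99, so 4. A category that can occur only in the MIS arm needs 15/333 = 4.5% of that arm to reach 3% of all 500 subjects.

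The probability of falling below the cut-off c is P(X ≤ c − 1), with X binomial(n MIS, true rate):

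| N (MIS) | Denominator of the 3% | c | True rate 3% | 4% | 5% |
|---|---|---|---|---|---|
| 500 (333) | all subjects | 15 | 92% | 64% | 30% |
| 500 (333) | MIS arm | 10 | 46% | 14% | 3% |
| 200 (133) | all subjects | 6 | 79% | 56% | 34% |
| 200 (133) | MIS arm | 4 | 43% | 22% | 10% |

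Reported directly, such a category would be informative. The exact (Clopper-Pearson) 95% interval is 1.4% to 5.5% for 10/333 = 3.0%, and 0.8% to 7.5% for 4/133 = 3.0%.

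For context on low rates, the protocol's background reports, for the surgical arm of an earlier phase III trial of catheter evacuation with thrombolysis, 2 bacterial brain infections in an arm of 250 (2/250 = 0.8%) and symptomatic bleeding in 2%. The procedure was different, so these figures only illustrate that complications of this kind can lie below 3%.

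**The case against.** The strongest reply is that the event is already well covered. Section 3 commits to monitoring the anticipated risks for changes in event rates, and this is one of them. Section 7.6.1 collects all AEs to discharge or day 7, and SAEs and neurological AEs to the final visit. Sections 7.6.1.3 and 7.6.1.4 attribute and grade each event against the index hemorrhage, the procedure and the device. Device-related events fall within the CEC's remit, and 12.2 sends all reported AEs and SAEs to the DSMB. The medical monitor may also call for source documents on other events. The CEC develops its own categories, and its charter and the DSMB's are not among the documents; either could name this event. All of this stands. It reduces the point to what is assured in the protocol.

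Three stronger readings are tempting, and the documents do not support them:
- A reader might infer that these injuries go unrecorded or unseen by the DSMB. The provisions above show otherwise.
- A reader might infer that a published surgical-complication rate will mislead. Neither document plans a rate from this category; the list triggers narratives, review and DSMB presentation.
- A reader might infer that the list contradicts Protocol 10.1. That passage is not tied to the list, and CEC-adjudicated relatedness to device and procedure could supply the complication rates.

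It is also fair to say that the 3% arithmetic measures a different matter from the list. It applies only if the sentence limits output, and SAP 11.2 can be read as tabulating every term. The arithmetic also treats the injury as one category, whereas coding by body system and preferred term could split it or pool it.

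Last, adding the injury to the list with the NIHSS rise of 4 used for the other events would fail in part. The NIHSS sensory item scores at most 2 (Protocol 16.3), so the isolated sensory deficit named in section 3 could not reach 4 points.

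**Conclusion.** Two limited gaps remain. First, the closed list in 7.6.1 and 12.2 leaves out a named surgical risk, so a narrative, medical-monitor review and separate DSMB presentation are not assured for it. This follows from the text alone and needs no assumed rate. Second, SAP 11.2 does not say that the defined events are reported whatever their frequency, and it gives no denominator for its cut-off. If the sentence limits output, an MIS-only category at an assumed true rate of 3% would be left out with probability 92% or 46% at N = 500, depending on the denominator.

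The primary efficacy inference and the 30-day mortality analysis are not affected. This is an inexpensive improvement to safety reporting, not a defect in the trial's main conclusions. The wording of the list is certain; the practical consequence is less so, because the CEC and DSMB charters may already deal with it.

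**What to change.** 1. In Protocol 7.6.1 and 12.2, add to the surgical-complication category: *new or worsened neurological or sensory deficit within 30 days attributed to unintended tissue removal or access/sheath injury*, adjudicated by the existing CEC. Do not require an NIHSS rise of 4 or more for the event to qualify; use that threshold, if at all, only to grade severity.
2. In SAP 11.2, state that all defined events, and all CEC-adjudicated device- or procedure-related events, are reported by arm regardless of the 3% cut-off. Report surgical complications as an MIS-arm rate with an exact 95% confidence interval. State the denominator of the 3% rule.

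The change is one phrase in two lists and a short addition to one SAP section, with no new visits, data collection or committee. The downside is a few more narratives, CEC reviews and table rows. The first attribution would still come from an unblinded site, in patients whose hemorrhage itself causes deficits, so CEC adjudication matters.
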